4.6.1.2 Presentation

Exposure to IP is summarised using descriptive statistics (mean, standard deviation, median, minimum and maximum) based on the FAS. In addition, the number of dosing occasions are also summarised on the FAS.

4.6.2 Adverse Events

4.6.2.1 Definitions and Derivations

Adverse events, categorised as Serious Adverse Events (SAEs), SAEs with outcome of death, Adverse Events leading to discontinuation of IP (DAEs), Adverse Events of special interest (AESIs) defined in the CSP Section 8.3.6, experienced by the participants were collected throughout the entire study and coded using the latest version of the Medical Dictionary for Regulatory Activities (MedDRA).

Adverse event data is categorized according to their onset date into the following study periods:

- AEs in the pre-treatment period are defined as those with onset day before day of first dose of study treatment.
- AEs in the on-treatment period are defined as those with onset day between the day of first dose of study treatment and earliest (date of last dose of IP + 33 days, date of death, date of study withdrawal).
- AEs in the post-treatment period are defined as those with onset after the end of ontreatment period defined above until the study completion or withdrawal date.
- AEs in the on-study period are defined as those with onset between day of first dose of study treatment and the study completion or withdrawal date.

If an AE has a missing onset date completely it is considered an on-treatment event unless the stop date of the AE indicates otherwise. Similarly, if an AE has a partial onset date it is considered an on-treatment AE unless the partial onset date or the stop date indicates otherwise.

AEs that have missing causality (after data querying) is assumed to be related to study drug.

Liver adverse events and evaluation of Hy's Law are submitted as a SAE and is described accordingly. Hy's Law cases are listed with their related laboratories parameters. Details regarding Potential Hy's Law and Hy's Law are given in the CSP Appendix F2.

Adjusted incidence rate

Exposure-adjusted incidence rate is defined as the total number of participants reporting adverse events experienced during the extent of exposure divided by total extent of exposure (irrespective of whether they have had the AE). The individual participant' extend of exposure (days) is calculated as presented in Section 4.6.1.1. The total participant-years

exposure is derived as the sum of the individual participant extent of exposure (days) divided by 365.25.

In all exposure-adjusted summaries of AEs, multiple occurrences of the same event for a particular participant are not counted as separate events. A participant is either considered to have no events of the type being summarised, or one or more occurrences of that event.

4.6.2.2 Presentation

Adverse events are summarised separately for the on-treatment and on-study periods unless specified otherwise. Adverse events occurring during the screening period, or occurring post-treatment is listed, but not summarised separately.

An overall summary table is produced showing the number and percentage of participants with at least 1 adverse event in any of the following categories: Serious Adverse Events (SAEs), SAEs with outcome of death, AEs leading to discontinuation of investigational product (DAEs). The number of events in the different AE categories is also presented. The summaries are accounted for multiple occurrences of the same event in a participant.

The number and percentage of participants with an SAE, SAEs with outcome of death and AESI (each category separately) are presented by System Organ Class (SOC) and Preferred Term (PT) assigned to the event using the MedDRA dictionary for on-treatment and onstudy period. For each PT, the number and percentage of participants reporting at least one occurrence is presented (i.e., multiple occurrences of an AE for a participant are only counted once). SOCs and PTs are sorted by international order (the Internationally Agreed Order of SOCs was developed for consistency irrespective of language or alphabet. The SOC order was based upon the relative importance of each SOC in AE reports). In addition, the exposure-adjusted SAE and AESI (each category separately) summaries are presented by SOC and PT. The number and percentage of participants with SAEs are presented sorted by decreasing frequency on PT level for on-treatment and on-study period. The DAE are presented by SOC and PT for on-treatment period only.

On-treatment SAEs, DAEs, and AESIs (each category separately) are also summarised by SOC, PT and causality/relatedness (as determined by the investigator). Information about maximum intensity, of AEs is listed. If a participant reports multiple occurrences within each PT, the maximum intensity is taken as the highest recorded (the order being mild, moderate, and severe) respectively.

Key subject information of SAEs, DAEs and AESIs for on-study is presented.

The handling of partial/missing dates for AEs is detailed in Appendix A. Duration of AEs is not calculated using imputed dates and instead set to missing.

The number and percentage of participants reporting COVID-19 AEs (as defined based on the COVID-19 MedDRA terms) is summarised by System Organ Class (SOC) and Preferred Term (PT) for the on-treatment and on-study periods.

In addition, if there are more than 10 participants reporting COVID-19 AEs, then the AE listing is repeated including only these participants, with details of all AEs reported by these participants.

All summaries are presented on the FAS.

Presentation of Adverse events for interim analysis

The number and percentage of participants with at least 1 adverse event in any of the following categories: Serious Adverse Events (SAEs), SAEs with outcome of death, AEs leading to discontinuation of investigational product (DAEs) is presented for on-study period. The number of events in the different AE categories is also presented.

The number and percentage of participants with SAEs are presented by System Organ Class (SOC) and Preferred Term (PT) as well as sorted by decreasing frequency on PT level for on-study period.

Key subject information of AESIs is presented.

All summaries for interim analysis are presented on the FAS.

4.6.3 Clinical Laboratory, Blood sample

4.6.3.1 Definitions and Derivations

Blood samples for determination of clinical chemistry, haematology and serology (Hepatitis B and C) parameters are taken at Visit 1 (Week -4 to Week 0) and assessed in a central laboratory. Central laboratory normal reference ranges are used for the identification of individual clinically important abnormalities, classified as low (below range), normal (within range or on the limits) or high (above range).

4.6.3.2 Presentations

Laboratory data are summarised by descriptive statistics (mean, standard deviation, median, lower and upper quartile, minimum and maximum). The clinically important abnormalities per categories presented in Section 4.6.3.1 are listed.

Laboratory data are presented on-study period only.

All data are summarised including data from unscheduled visits and repeated measurements according to the visit window presented in Section 3.3.2.

4.6.4 Clinical Laboratory, Urinalysis

4.6.4.1 Definitions and Derivations

Urine HCG is performed only for female participants at the times detailed in the CSP.

4.6.4.2 Presentations

No results will be listed/summarised, the analysis of positive results remains outside the scope of this Statistical Analysis Plan.

4.6.5 Other Laboratory, Evaluations

4.6.5.1 Definitions and Derivations

Other laboratory tests are applicable to female participants only and conducted at Visit 1 (Week -4 to 0). Serum β -HCG and Follicle-stimulating hormone for female participants lower than 50 years who have been amenorrhoeic for \geq 12 months.

4.6.5.2 Presentations

No results will be listed/summarised, the analysis of positive results remains outside the scope of this Statistical Analysis Plan.

4.6.6 Vital Signs

4.6.6.1 Definitions and Derivations

The weight and height are measured according to the schedule described in CSP Section 1.3. BMI is calculated according to the formula presented in Section 4.1.5. Absolute change from baseline is calculated as described in Section 3.3 for weight and BMI.

4.6.6.2 Presentations

Observed values of weight, height and BMI are summarised at each timepoint they are measured by means of descriptive statistics (mean, standard deviation, median, lower and upper quartile, minimum and maximum). The on-study period is used to summarise the data. In addition, for weigh and BMI absolute change from baseline is also presented over time.

4.6.7 Electrocardiogram

4.6.7.1 Definitions and Derivations

Not collected.

4.6.7.2 Presentations

Not applicable

4.6.8 Other Safety Assessments

Not applicable

5 INTERIM ANALYSIS

An interim analysis may be performed if approximately 50 participants complete V4 before a data cut-off date planned on mid-April 2023. All data available for participants who completed Visit 4 prior to the data cut-off date will be included. The results are not used to change any element of the study design and the study continues regardless of the results of interim analysis.

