9.5 Interim Analyses

An interim analysis may be performed if approximately 50 participants complete Visit 4 before a data cut-off date planned on mid-April 2023. In case of interim analysis, all data available for those participants will be included in summaries. The analysis will address key efficacy and safety objectives during the OCS titration period for the purpose of publication. The results will not be used to change any element of the study design and the study will continue regardless of the results of interim analysis. The SAP will be amended to describe the interim analysis in more details.

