3.2.2 Full Analysis Set

Includes all enrolled participants who received at least one dose of tezepelumab, irrespective of their protocol adherence and continued participation in the study. Participants are analysed irrespective of whether they prematurely discontinue, according to the intent-to-treat principle. Participants who withdraw from the study are included up to the date of their study termination.

All efficacy, demographics, baseline characteristics, and safety analyses are performed using the FAS.

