3.3 General Considerations

In general, continuous endpoints are summarised using the mean, the standard deviation, median, minimum value, and maximum value, and the categorical endpoints are summarised using frequency counts and percentages, as well as a two-sided 95% CI for proportions computed using exact Clopper-Pearson method. Time to event data is presented graphically using Kaplan Meyer curve.

Absolute change from baseline is defined as (post-baseline value – baseline value). The percent change from baseline is defined as {(post-baseline value – baseline value)/baseline value)}*100. Baseline calculations are defined in the Section 3.3.1.2.

For participants' proportion calculation, the denominator is the number of participants in the Full Analysis Set defined in Section 4.1.2 unless otherwise stated.

No imputation performed beyond the approach defined for outcome measures. Imputation for partial date is detailed in the Appendix A.

Unless specified otherwise, the daily maintenance OCS dose, including the daily OCS at baseline (Section 3.3.1.2) and the final daily OCS dose (Section 4.2.1.2), is defined based on the prescribed maintenance dose of OCS, expressed as a dose per day, at the time of the relevant visit. If a participant is on a fixed daily dose, then the OCS dose is defined as that prescribed dose. If the participant is on every other day regimen (or different doses every other day), then the OCS dose is defined as the average amount prescribed to be taken each day. For example, should a participant be on a 10 mg every other day regimen of OCS, their OCS dose is defined as 5 mg.

Maintenance dose of OCS is collected on the ECSYSCRT eCRF page with a therapy reason of "Asthma maintenance dose", "Titration, due to asthma", "AI based on cortisol test", "Signs/symptoms of AI" and "Adrenal crisis". If the maintenance OCS doses with more than one therapy reasons (including only those mentioned earlier) are prescribed on the same day (e.g., "Asthma maintenance dose" and in addition "Signs/symptoms of AI"), then the sum of the doses are calculated.

Note that the prescribed OCS dose with therapy reason of "Asthma exacerbation per protocol" or "Worsening of asthma, without exacerbation" is not included in the daily OCS dose calculation. In case of overlapping OCS doses taken for asthma worsening or exacerbation with maintenance doses of OCS, the latter one is excluded from the daily OCS dose calculation.

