4.2.1.8 Interim Analysis of Primary Endpoint

The derivation of the final daily maintenance OCS dose as described in Section 4.2.1.2 cannot be applied due to the reason mentioned in Section 4.2. Alternatively, for each post-baseline visit the latest daily maintenance OCS dose at the time of the visit is used as described in Section 4.2.7.2.

The number and proportion of participants who discontinued OCS or reduced OCS dose to ≤ 5 mg/day is summarised over time on the FAS.

4.2.2 Secondary Endpoint - Annual asthma exacerbation rate (AAER) over Week 28 and Week 52

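### The optional interim analysis for publication takes its data from Visit 4 completers, but its efficacy and adverse event tables are labelled FAS, which is everyone dosed

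*SAP*

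**What the plan says.** The trigger for the interim analysis is in SAP section 5: "An interim analysis may be performed if approximately 50 participants complete V4 before a data cut-off date planned on mid-April 2023". The next sentence sets the data: "All data available for participants who completed Visit 4 prior to the data cut-off date will be included". Protocol 9.5 agrees. After naming the roughly 50 participants who complete Visit 4, it says "In case of interim analysis, all data available for those participants will be included in summaries", and it gives the aim: "The analysis will address key efficacy and safety objectives during the OCS titration period for the purpose of publication".

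The tables carry a different population label. SAP 4.2.1.8 says that the proportion who stopped OCS or reached 5 mg/day or less "is summarised over time on the FAS". The same label is attached to the interim results for OCS reduction and change, FEV1, ACQ-6, biomarkers and cumulative corticosteroid dose (SAP 4.2.5.7, 4.2.7.7, 4.2.8.7, 4.2.9.7, 4.2.12.7, 4.2.15.7 and 4.2.21.7). For adverse events, SAP 4.6.2.2 closes with "All summaries for interim analysis are presented on the FAS". By default, for proportions, "the denominator is the number of participants in the Full Analysis Set" (SAP 3.3).

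SAP 3.2.2 defines that set: "Includes all enrolled participants who received at least one dose of tezepelumab, irrespective of their protocol adherence and continued participation in the study". SAP 3.2 has no separate interim set, and no text adds back dosed participants who lack Visit 4. Interim disposition is the exception: SAP 4.1.1.2 puts it on the All participants analysis set.

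**The concern.** Visit 4 falls eight weeks after the first dose. A rule that admits participants because they completed it selects on what happened after treatment began, and what happened may be the very outcome that the tables should report. A participant who dies in Week 5, or has a serious event in Week 3 and withdraws, never completes Visit 4. As section 5 is written, that event is outside the data for the interim SAE, death and DAE tables, while the label tells the reader that everyone dosed is there. The OCS proportions are likewise calculated among those who stayed to Week 8.

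Because the interim is meant for publication, outside readers would take the FAS label at face value. With about 50 participants, a handful of missing people is visible in the percentages.

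**Working it through.** **Comparing the texts.** The interim data are those of dosed participants who completed Visit 4 before the cut-off. The FAS is all dosed participants. The two sets coincide only if every dosed participant has completed Visit 4 by the cut-off. Those in the second set but not the first are of two kinds:

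- Participants not yet due for Visit 4. This omission is administrative and less likely to bias.
- Participants who were due but have no Visit 4: deaths, study withdrawals, discontinuers on follow-up option 2 (telephone and ePRO) or option 3 (one call at 52 weeks) in Protocol 7.1, and missed visits. This omission depends on the course after dosing.

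A participant who stops tezepelumab but takes option 1 keeps attending clinic, can complete Visit 4 and stays in.

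**The plan's own precision figure.** Protocol Table 12 gives a Clopper-Pearson half-width at 50% of ±5.8 points for N=300 and ±14.5 for N=50. Exact limits from beta quantiles give ±5.80 and ±14.47, so both figures reproduce. The N=50 figure is the relevant yardstick for the interim.

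**Size, by illustration.** Inputs:

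- n = 50 completers (SAP section 5).
- Success proportion p = 50%, which is 25/50. This is the sample-size assumption in Protocol 9.2, borrowed here and not a forecast for Week 8.
- k = dosed participants who were due but have no Visit 4. The documents give no figure, so k = 0 to 5 is an assumption; it corresponds to a loss of 0/50 = 0% to 5/55 = 9.1%.

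If the k participants count as non-successes, the proportion is 25/(50 + k) and the shift is p × k/(50 + k). For DAEs, take 0/50 among completers and, as the worst case, a DAE in each of the k, giving k/(50 + k).

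| k | Success proportion (95% CI) | Shift, points | DAEs, worst case (95% CI) |
|---|---|---|---|
| 0 | 25/50 = 50.0% (35.5 to 64.5) | 0 | 0/50 = 0% (0 to 7.1) |
| 1 | 25/51 = 49.0% (34.8 to 63.4) | 1.0 | 1/51 = 2.0% (0.0 to 10.4) |
| 3 | 25/53 = 47.2% (33.3 to 61.4) | 2.8 | 3/53 = 5.7% (1.2 to 15.7) |
| 5 | 25/55 = 45.5% (32.0 to 59.4) | 4.5 | 5/55 = 9.1% (3.0 to 20.0) |

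The efficacy shift is small beside the ±14.5 points of sampling error. The safety effect is different in kind: in the k = 5 row, a table showing no DAEs would stand for a cohort with five.

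**Direction for efficacy.** The non-success rule is itself an assumption. SAP 4.2.1.8 does not say how a dosed participant without the visit is scored, and SAP 4.2.1.3 rules out imputation. Entry at 5 mg/day is allowed (Protocol 5.1), so someone who leaves early may already be at 5 mg/day or less. If all five leavers counted as successes, the proportion would be (25 + 5)/55 = 54.5%.

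**The case against.** The best reply is that neither document says that only completers' data enter. On that reading the FAS label and the default denominator govern, and people who left before Visit 4 are in. The SAP itself does not apply the completer rule everywhere, since interim disposition uses all screened participants. This stands in part: it shows that the texts conflict. It does not settle the conflict, because section 5 is the specific interim rule and Protocol 9.5 repeats it.

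Several stronger inferences are tempting, and the documents do not support them:

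- *That all early discontinuers are removed.* Option 1 participants can remain, so the group lost is dosed participants without Visit 4.
- *That early exits disappear from the report.* Interim disposition covers treatment discontinuations and study withdrawals with reasons. It may show the exits, though it does not return the events to the adverse event tables.
- *That each missing person is worth two efficacy points.* At 50% the shift for one leaver counted as a non-success is about 1 point. About 2 points applies to a rare event counted from near zero.
- *That the corrected figures must be less favourable.* The direction for efficacy depends on a scoring rule that the SAP does not give.

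The interim is also optional, tests no hypothesis and changes no design element. That limits the consequence to the interim publication.

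**Conclusion.** The inconsistency holds: the stated interim data are those of Visit 4 completers, and the label says everyone dosed. As written, a death, SAE or DAE followed by exit before Week 8 is outside the interim safety tables. That is the part with real weight; the efficacy effect is secondary.

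The size cannot be determined from the documents. Under the assumption of 0 to 5 dosed participants without Visit 4 per 50 completers, it runs from nothing to 4.5 points on a 50% success proportion if they count as non-successes, and from 0% to 9.1% for DAEs in the worst case. The actual effect may be zero. The analyses at Week 28 and Week 52 do not use this rule and are unaffected. The point should be corrected, but it does not threaten the trial's main results.

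**What to change.** Change SAP section 5 and Protocol 9.5 together, so that they stay aligned:

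1. Select by calendar: all FAS participants first dosed at least 8 weeks + 5 days (56 + 5 = 61 days, allowing for the visit window) before the cut-off, whether or not Visit 4 was completed.
2. State how participants without the visit count in the OCS proportions.
3. Present interim safety for everyone dosed by the cut-off.

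SAP edition 5.0 is dated 9 November 2023, after the planned mid-April 2023 cut-off, so the interim may already exist; the documents do not say. If it does, reissue it on the calendar-based set. Alternatively, label it 'Visit 4 completers' and report how many dosed participants were excluded, why, and their SAEs, DAEs and AESIs.

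The cost is a short edit to two documents and, if tables exist, a small re-analysis. Published figures may change slightly.

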7 APPENDIX

Appendix A Partial dates for adverse events and prior/concomitant medications

Dates missing the day, or both the day and month of the year adhere to the following conventions to classify treatment-emergent AEs (TEAEs) and to classify prior/concomitant medications:

- The missing start day is set to:
 - First day of the month of occurrence, if the start YYYY-MM is after the YYYY-MM of first study treatment
 - The day of the first study treatment, if the start YYYY-MM is the same as YYYY-MM of the first study treatment
 - The date of informed consent, if the onset YYYY-MM is before the YYYY-MM of the first study treatment.
- The missing end day is set to:
 - The last day of the month of the occurrence, if the end YYYY-MM is after the YYYY-MM of the first study treatment.
 - o Death date if the participant died in the same month.
 - The day of last study treatment if the YYYY-MM of occurrence is the same as the last study treatment.
- If the start date is missing both the day and month, the start date is set to:
 - o January 1 of the year of occurrence.
 - The date of the first study treatment, if the start year is the same as the year of the first study treatment
- If the end date is missing both the day and month, the date is set to:
 - o December 31 of the year of occurrence.
 - o Date of death if the participant died in the same year.
 - Last study treatment date if the year of occurrence is the same as the last study treatment date.

- If the start date is null, the date is set to:
 - o The date of first study treatment.
 - o January 1 of the same year as the end date, if the end date suggests that the start date could be prior to the date of first study treatment.
- If the end date is null and not recorded as ongoing, the date is set to:
 - The date of the first study treatment, if the start date is prior to the date of first study treatment.
 - The date of last visit, if the start date is on or after the date of first study treatment.
- If the end date is null and recorded as ongoing, the end date is not imputed.

SIGNATURE PAGE

This is a representation of an electronic record that was signed electronically and this page is the manifestation of the electronic signature

Document Name: d5180c00	037-sap-wayfinder-ed-5	
Document Title:	Statistical Analysis Plan Edition	1 5
Document ID:	Doc ID-004819648	
Version Label:	5.0 CURRENT LATEST APPROVED	
Server Date (dd-MMM-yyyy HH:mm 'UTC'Z)	Signed by Meaning of Signature	
